3.1. Variables

The following table lists all variables relevant to the analysis along with their ICD, OPS or ATC codes. For each patient, possible comorbidities will be recorded at baseline by including all outpatient and inpatient information coded within two years prior to the index hospitalization and during first hospitalization (exceptions are marked accordingly).

The "minor outpatient complications" defined below (see the last row of the following table) will be based exclusively on outpatient information coded after discharge of the first hospitalization.

All other variables concerning complications during follow-up will be collected exclusively from inpatient information during hospitalization and after discharge.

Variable	Classification	Code
Olecranon fracture	ICD	S52.01
Simple fracture TBW	OPS	5-793.27
Multi-fragmented TBW	OPS	5-794.17
Simple fracture LPF	OPS	5-793.k7
Multi-fragmented LPF	OPS	5-794.k7
Comorbidities at Baseline		
Alcohol abuses	ICD	E24.4, F10, G31.2, G62.1, G72.1, I42.6, K29.2, K70, K85.2, K86.0, T51.0, T51.9
Arthrosis	ICD	M15-M19 (only before index admission)
Atherosclerosis	ICD	I70
Atrial fibrillation and flutter	ICD	I48
Asthma		J45
Bone tumor/metastasis	ICD	C40.0, C79.5, C79.86, C79.9
Cancer	ICD	C
Chronic kidney disease	ICD	N18, N19
Chronic polyarthritis	ICD	M05, M06
Congestive heart failure	ICD	I50
Coronary heart disease	ICD	I25
Dementia	ICD	F00, F01, F02, F05.1, G30, G31.1
Depressive episode	ICD	F32, F33
Diabetes mellitus	ICD	E10-E14
Dorsalgia	ICD	M54
Hypertension	ICD	I10-I15
Infection	ICD	M86.02, M86.12, M86.22, M86.32, M86.42, M86.52, M86.62, M86.82, M86.92, T84.5, T84.6, T84.7 (only before index admission)
Neurotic, stress-related and somatoform disorders	ICD	F41, F43, F45
Nicotine abuses	ICD	F17
Obesity	ICD	E66
Osteoporosis	ICD	M80-M85
Parkinson	ICD	G20
Polytrauma	ICD, OPS, DRG	ICD: T07 , OPS: 5-982 , or coded DRG started with "W" (only during index hospitalization)
Elbow arthrosis	ICD	M25.52 (only before index admission)
Previous stroke	ICD	I60-I69 (only before index admission)
Prior level of care (LoC)		Level of care in the database (from 2017)
Problems related to care-provider dependency	ICD	Z74

Pharmaceutical therapy		
Any anticoagulant	ATC	B01AA, B01AB, B01AC, B01AE, B01AF, B01AX
Vitamin D or calcium	ATC	A11CC
Bisphosphonates	ATC	M05BA, M05BB
Any osteoporosis pharmacotherapy	ATC	Vitamin D/Calcium or Bisphosphonates
Contraceptives for topical use	ATC	G02B (only for matching)
Hormonal contraceptives for systemic use	ATC	G03A (only for matching)
General Complications		
Acute liver failure	ICD	K72.0, K72.7, K72.9
Acute myocardial infarction	ICD	I21, I22
Acute renal failure	ICD	N17
Acute respiratory distress syndrome	ICD	J80
Cardiac arrest	ICD	I46
Deep vein thrombosis	ICD	I80.1, I80.2, I82.2, I82.3
Delirium	ICD	F05
Pulmonary embolism	ICD	I26
Sepsis	ICD	A41, A40, B37.7, R65.0, R65.1, R65.9, R57.2
Stroke	ICD	I60-I64
Ischemic stroke	ICD	I63-I64
Resuscitation	OPS	8-77 (also defined as complication, if it happens on the same day as surgery)
Intensive care	OPS	8-980, 8-98f (only during hospital stay)
Blood transfusion	OPS	8-800.0, 8-800.1, 8-800.c (only during hospital stay)
Surgical complications (at least one day after surgery)		
Conversion to TBW	OPS	5-793.27, 5-794.17
Conversion to LPF	OPS	5-794.k7, 5-793.k7
Endoprosthetic joint and bone replacement	OPS	5-824.40, 5-824.41, 5-824.50, 5-824.51, 5-824.52
Conversion to other fracture fixation	OPS	5-790.07, 5-790.17, 5-790.27, 5-790.37, 5-790.47, 5-790.57, 5-790.67, 5-790.97, 5-790.d7, 5-790.k7, 5-790.m7, 5-790.n7, 5-790.p7, 5-790.x7, 5-793.17, 5-793.37, 5-793.67, 5-793.77, 5-793.87, 5-793.97, 5-793.a7, 5-793.b7, 5-793.c7, 5-793.g7, 5-793.h7, 5-793.m7, 5-793.n7, 5-793.x7, 5-794.07, 5-794.27, 5-794.57, 5-794.67, 5-794.77, 5-794.87, 5-794.a7, 5-794.b7, 5-794.c7, 5-794.g7, 5-794.m7, 5-794.n7, 5-794.x7
Conversion, any	OPS	Any conversion as defined above
Upper limb amputation, ipsilateral (exarticulation elbow or forearm)	OPS	5-862.2, 5-862.3, 5-862.4
Bursitis	ICD	M70.2, M70.3 (only during hospital stay)
Compartment syndrome	ICD	S51.86 (only during hospital stay)

Consequences of injury of the upper extremity	ICD	T92.1 (only during hospital stay)
Haematoma after surgery	ICD	T81.0 (only during hospital stay)
Implant dislocation	ICD	T84.11 (only during hospital stay)
Mechanical malfunction or material failure/loosening	ICD	T85.88, T85.9 (only during hospital stay)
Peri-prosthetic or peri-implant fracture	ICD	M96.6, T84.11 (only during hospital stay)
Surgical incidents	ICD	Y69, Y82.8, Y84.9 (only during hospital stay)
Delayed union (if coded within six months)	OPS	5-781.a7, 5-782.17, 5-782.27, 5-782.37, 5-782.47, 5-782.57, 5-782.a7, 5-782.b7, 5-782.x7, 5-784.07, 5-784.17, 5-784.27, 5-784.37, 5-784.47, 5-784.77, 5-784.87, 5-784.b7, 5-784.c7, 5-784.d7, 5-784.e7, 5-784.f7, 5-784.x7
Infection	ICD	T84.5, T84.6, T84.7, M86.02, M86.12, M86.22, M86.32, M86.42, M86.52, M86.62, M86.82, M86.92 (only during hospital stay)
	OPS	5-780.47, 5-780.57, 5-780.67, 5-780.77, 5-780.87, 5-780.97, 5-785.17, 5-785.57, 5-785.77, 5-800.24, 5-800.25, 5-800.34, 5-800.35, 5-800.a4, 5-800.a5, 5-800.b4, 5-800.b5, 5-810.14, 5-810.15, 5-810.74, 5-810.75, 5-810.84, 5-810.85, 5-850.h2, 5-850.j2, 5-892.37, 5-892.47, 5-896.27, 8-989, 8-989.0, 8-989.1, 8-989.2, 8-989.3, 8-989.4, 8-989.5, 8-989.6
Infection, resistant	ICD	U80-83 (only during hospital stay)
	OPS	8-987
Joint damage / cartilage damage	OPS	5-780.37, 5-784.57, 5-784.67, 5-800.84, 5-800.85, 5-810.44, 5-810.45, 5-812.04, 5-812.05, 5-812.34, 5-812.35, 5-812.94, 5-812.95, 5-812.a4, 5-812.a5, 5-812.e4, 5-812.e5, 5-812.f4, 5-812.f5, 5-812.g4, 5-812.g5, 5-812.h4, 5-812.h5, 5-812.k4, 5-812.k5, 5-812.m4, 5-812.m5
Luxation	OPS	8-201.4, 8-201.5 (also including outpatient sector after discharge)
Malunion	OPS	5-781.07, 5-781.17, 5-781.27, 5-781.37, 5-781.47, 5-781.57, 5-781.67, 5-781.77, 5-781.87, 5-781.97
Nerve injury	OPS	5-040.1, 5-040.2, 5-040.3, 5-041.1, 5-041.2, 5-041.3, 5-044.1, 5-044.2, 5-044.3, 5-045.1, 5-045.2, 5-045.3, 5-046.1, 5-046.2, 5-046.3, 5-047.1, 5-047.2, 5-047.3, 5-048.1, 5-048.2, 5-048.3, 5-049.1, 5-049.2, 5-049.3, 5-04b.1, 5-04b.2, 5-04b.3, 5-050.1, 5-050.2, 5-050.3, 5-051.1, 5-051.2, 5-051.3, 5-052.1, 5-052.2, 5-052.3, 5-053.1, 5-053.2, 5-053.3, 5-054.1, 5-054.2, 5-054.3, 5-055.1, 5-055.2, 5-055.3, 5-056.1, 5-056.2, 5-056.3, 5-057.1, 5-057.2, 5-057.3 (only during hospital stay)
Non-union / Pseudoarthrosis (if coded after six months)	OPS	5-781.a7, 5-782.17, 5-782.27, 5-782.37, 5-782.47, 5-782.57, 5-782.a7, 5-782.b7, 5-784.07, 5-784.17, 5-784.27, 5-784.37, 5-784.47, 5-784.77, 5-784.87, 5-784.b7
Osteonecrosis	ICD	M87.22, M87.32, M87.82, M87.92
Postoperative stiffness, Adhesive capsulitis, Frozen elbow	OPS	5-800.64, 5-800.65, 5-800.c4, 5-800.c5, 5-810.24, 5-810.25, 5-810.94, 5-810.95

Vascular injury	OPS	5-388.12, 5-395.12, 5-397.12 (only during hospital stay)
Secondary surgery, open (LPF and TBW)	OPS	5-780.07, 5-780.17, 5-780.27, 5-780.37, 5-780.67, 5-780.x7, 5-782.17, 5-782.27, 5-782.37, 5-782.47, 5-782.57, 5-782.a7, 5-784.07, 5-784.17, 5-784.27, 5-784.37, 5-784.47, 5-784.57, 5-784.67, 5-784.77, 5-784.87, 5-784.a7, 5-784.b7, 5-785.07, 5-785.17, 5-785.27, 5-785.37, 5-785.47, 5-785.57, 5-785.67, 5-785.77, 5-789.b7, 5-789.c7, 5-794.07, 5-794.27, 5-794.57, 5-794.67, 5-794.77, 5-794.87, 5-800.14, 5-800.15, 5-800.34, 5-800.35, 5-800.44, 5-800.45, 5-800.54, 5-800.55, 5-800.74, 5-800.75, 5-800.84, 5-800.85, 5-800.94, 5-800.95, 5-800.x4, 5-800.x5, 5-801.04, 5-801.05, 5-801.34, 5-801.35, 5-801.44, 5-801.45, 5-801.b4, 5-801.b5, 5-801.c4, 5-801.c5, 5-801.g4, 5-801.g5, 5-801.h4, 5-801.h5, 5-801.k4, 5-801.k5, 5-801.m4, 5-801.m5, 5-801.n4, 5-801.n5, 5-801.p4, 5-801.p5, 5-850.02, 5-850.12, 5-850.22, 5-850.32, 5-850.42, 5-850.52, 5-850.62, 5-850.72, 5-850.82, 5-850.92, 5-850.a2, 5-850.b2, 5-850.c2, 5-850.d2, 5-850.e2, 5-850.f2, 5-850.g2, 5-850.h2, 5-850.j2, 5-851.12, 5-851.22, 5-851.32, 5-851.42, 5-851.52, 5-851.62, 5-851.72, 5-851.82, 5-851.92, 5-851.a2, 5-851.b2, 5-851.c2, 5-851.d2, 5-852.02, 5-852.12, 5-852.22, 5-852.32, 5-852.42, 5-852.52, 5-852.62, 5-852.72, 5-852.82, 5-852.92, 5-852.a2, 5-852.b2, 5-852.c2, 5-852.d2, 5-852.h2, 5-852.j2, 5-853.02, 5-853.12, 5-853.22, 5-853.32, 5-853.42, 5-853.52, 5-853.62, 5-853.72, 5-853.82, 5-853.92, 5-853.x2, 5-855.02, 5-855.12, 5-855.22, 5-855.32, 5-855.42, 5-855.52, 5-855.62, 5-855.72, 5-855.82, 5-855.92, 5-855.a2, 5-855.b2, 5-859.02, 5-859.12, 5-862.2, 5-862.3, 5-862.4, 5-892.07, 5-892.17, 5-892.27, 5-892.37, 5-892.47, 5-896.07, 5-896.17, 5-896.27
Secondary arthroscopy (LPF and TBW)	OPS	5-782.b7, 5-784.c7, 5-784.d7, 5-784.e7, 5-784.f7, 5-810.04, 5-810.05, 5-810.14, 5-810.15, 5-810.24, 5-810.25, 5-810.44, 5-810.45, 5-810.54, 5-810.55, 5-810.64, 5-810.65, 5-810.74, 5-810.75, 5-810.84, 5-810.85, 5-810.94, 5-810.95, 5-810.x4, 5-810.x5, 5-811.24, 5-811.25, 5-811.34, 5-811.35, 5-811.44, 5-811.45, 5-811.x4, 5-811.x5, 5-812.04, 5-812.05, 5-812.34, 5-812.35, 5-812.94, 5-812.95, 5-812.a4, 5-812.a5, 5-812.e4, 5-812.e5, 5-812.f4, 5-812.f5, 5-812.g4, 5-812.g5, 5-812.h4, 5-812.h5, 5-812.k4, 5-812.k5, 5-812.m4, 5-812.m5, 5-812.x4, 5-812.x5, 5-819.04, 5-819.05, 5-819.14, 5-819.15, 5-819.x4, 5-819.x5
Implant removal (LPF)	OPS	5-787.07, 5-787.17, 5-787.37, 5-787.67, 5-787.77, 5-787.g7, 5-787.k7, 5-810.34, 5-810.35
Implant removal (TBW)	OPS	5-787.07, 5-787.17, 5-787.27, 5-787.67, 5-787.77, 5-787.g7, 5-810.34, 5-810.35
Revision of the osteosynthesis (LPF and TBW)	OPS	5-785.07, 5-785.17, 5-785.27, 5-785.37, 5-785.47, 5-785.57, 5-785.67, 5-785.77, 5-789.37, 5-78a.07, 5-78a.17, 5-78a.27, 5-78a.57, 5-78a.67, 5-78a.77, 5-78a.87, 5-78a.97, 5-78a.c7, 5-78a.g7, 5-78a.k7, 5-78a.m7, 5-78a.n7, 5-78a.x7, 5-793.07, 5-793.17, 5-793.27, 5-793.37, 5-793.67, 5-793.77, 5-793.87, 5-793.97, 5-793.a7, 5-793.b7, 5-793.c7, 5-793.g7, 5-793.h7,

		5-793.k7, 5-793.m7, 5-793.n7, 5-793.x7, 5-794.07 , 5-794.17, 5-794.27, 5-794.57, 5-794.67, 5-794.77, 5-794.87, 5-794.a7, 5-794.b7, 5-794.c7, 5-794.g7, 5-794.h7, 5-794.k7, 5-794.m7, 5-794.n7, 5-794.x7, 5-824.4 , 5-824.5, 5-825.01 , 5-825.4, 5-825.a, 5-825.m
Resection arthroplasty (for spacer placement)	OPS	5-829.4
Secondary arthroplasty	OPS	5-824.4 , 5-824.5
Arthrolysis	OPS	5-800.64 , 5-800.65, 5-810.24 , 5-810.25, 5-810.94, 5-810.95
Classification of complications and long-term endpoints/events		
Major adverse event		resuscitation, cardiac arrest, myocardial infarction, stroke, acute renal failure, acute liver failure, acute respiratory distress syndrome, sepsis or death from any case
Thromboembolic event		Deep vein thrombosis, pulmonary embolism, ischemic stroke or death from any case
Surgical complications		Adhesive capsulitis, arthrolysis, debridement, frozen elbow, implant removal within first 3 months, infection, infection with antibiotic-resistant germs, joint damage/cartilage damage, luxation, delayed union, non-union/pseudoarthrosis, malunion, nerve injury, vascular injury, osteonecrosis, postoperative stiffness, secondary arthroplasty, secondary arthroscopy, secondary surgery (open) including revision surgery, upper limb amputation
Implant-associated complications (IAC)		Impingement, bursitis, mechanical malfunction or material failure/loosening, periprosthetic or periimplant fracture
Non-implant associated complications (non-IAC)		Infection, infection with antibiotic-resistant germs, hematoma after surgery
Minor outpatient complications (LPF and TBW) ¹	ICD	G56.1, G56.2, G56.3, I80.80, I80.81, M00.02 , M00.12, M00.22, M00.82, M00.92, M13.12, M13.82, M13.92, M19.12, M19.22, M19.82, M19.92, M24.02, M24.12, M24.22, M24.32, M24.42, M24.52, M24.62, M24.82, M24.92, M25.12, M25.22, M25.32, M25.42, M25.52, M25.62, M25.72, M25.82, M25.92, M61.02, M61.12, M61.22, M61.42, M61.52, M61.92, M62.02, M62.12, M62.22, M62.32, M62.42, M62.52, M62.62, M62.82, M62.92, M65.02, M65.12, M65.22, M65.82, M65.92, M84.02, M84.22, M84.32, M84.82, M84.92, M86.12, M86.22, M86.32, M86.42, M86.62, M86.82, M86.92, M87.22, M87.32, M87.82, M87.92, M89.52, M96.6, T79.60 , T81.4, T84.01, T84.11, T84.5, T84.6, T84.7
	OPS	All outpatient codes OPS for LPF or TBW coded collected above

Table 2: Definition of all variables

¹ Data collection exclusively based on outpatient information coded after discharge.

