3.3. Possible sources of bias due to variable definition

In-hospital complications will be defined by the above reported codes that are coded in the same inpatient case as the surgery of OF (i.e. the index case series). For all OPS codes, the date has to be later in course of hospitalization than the surgery of OF (datum surgery with LPF/TBW < datum OPS code). ICD codes are all coded at the date of discharge and no chronological order within one case will be available. However, the defined complications are of such a serious nature that they always represent an unfavorable scenario from the patient's point of view, irrespective of the chronological course during hospitalization. It can also be assumed that, preoperatively, they did not represent a contraindication for surgery, if they were present before. Thus, it can be firstly assumed that complications predominantly occurred after surgery and, secondly, that any bias from (a few) events happens before surgery should be very low. In summary, all ICD codes for the above-mentioned complications that will be coded during the index case will be considered as in-hospital complications.

For all SC, only OPS ipsilateral coded procedures will be considered as complications. For ICD codes, no laterality will be available and thus, SC during follow-up will be mostly defined on OPS codes. For

osteonecrosis, however, it is therefore possible to wrongly count contralateral events as a complication which might add some bias, but both groups will be effected in the same manner.

4. Statistical Methods

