4.2. Analysis of Primary and Secondary Endpoints

To analyze differences in the treatment groups (TBW versus LPF), a 1:1 propensity score (PS) matching will be performed to guarantee sufficient balance between them. Each patient treated with TBW will be matched with a patients treated with LPF, based on age, sex, fracture complexity, year of treatment, all clinical relevant comorbidities and pharmaceutical therapy at index hospitalization (listed in table 2 “Comorbidities at Baseline” and “Pharmaceutical therapy”). Analysis set will defined by all patients included in the matching.

The balance will be evaluated using risk differences, z-differences and sum of squared z-differences (SSQZ) and will be reported for all variables before and after matching. The hyper-parameter (i.e. caliper with, distance for continuous variables, factors with exact matching) of the PS matching will be chosen in such way that the sum of squared z-differences (SSQZ) will be minimized around the number of variables included in the matching procedure (k), i.e.

$$k/2 \leq SSQZ \approx k.$$

Overlap between matching groups will be presented by the histogram of $logit(p_s)$. The dependency of the Matching partners and thus a stratified evaluation will not be considered.

In-hospital complications and 30-days mortality

All in-hospital endpoints as well as 30-day mortality are given by binary variables. Absolute and relative frequencies for both treatment group will be reported and differences between them will be tested via two-sided χ^2 -independence test. Moreover, a multivariable logistic regression model will be performed to adjust for patient's risk profile. Odds ratio (OR) comparing TBW and LPF for all in-hospital complications and 30-day mortality will be illustrated using forest plots.

30-day mortality will be defined as primary endpoint instead of in-hospital death to avoid bias due to differences in the LOS of both treatment groups. Absolute and relative frequencies for in-hospital death will be reported for the sake of completeness; however, p-values for possible differences will not be interpreted in a confirmatory manner.

Complications during follow-up

The start of observation will be defined by the day of surgery. Median follow-up time will be determined for the entire analysis set using Kaplan Meier estimate (death as censored event).

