For **OS, MAE and TE**, the Kaplan-Meier estimator will be determined for both groups and plotted for the survival functions along with unadjusted 95% confidence intervals (95%CI). Furthermore, at different time points (1 month, 3 months, 1-5 years), the event rates (1- survival function) will be reported with 95%CI and the total number of observed events per group. For the comparison of groups, the Log rank test will be conducted. Multivariable Cox regression models will analyze the impact of baseline variables on the endpoints. The resulting hazard ratios (HRs) will be presented along with its unadjusted 95% confidence intervals and illustrated in forest plots.

For **SC and minor outpatient complications**, death will be considered as a competing risk event. Hence, cumulative incidence function (CIF) determined by Aalen-Johansen estimate and sub-distributional hazards using Fine & Gray Cox models² will be calculated. Groups will be compared with Gray's test. All results were presented in an analog way explain above (plot of CIFs, reporting of CIF at different time points, forest plot for the HRs).

Multiple comparison problem

As mentioned above, patients were grouped by age (i.e. 18-44 years, 45 – 69 years, ≥ 70 years), where younger (<70 years) and older patients (≥ 70 years) will be analyzed (and published) in separate studies. To account for the multiple test problem in each study separately (<70 years and ≥ 70 years), all p-values comparing treatment-effects determined from multivariable analysis of all primary endpoint will be jointly adjusted using Bonferroni-Holm method³ to control the family-wise error rate with respect to the multiple comparison problem. Adjusted p-values will be compared with the overall significance level of 5%.

Time-dependent analysis

Should the evaluation reveal an overlap of the survival curves approximated with Kaplan-Meier, we will further investigate these with a time-dependent survival analysis or landmark analysis with suitably chosen cut-off values. In addition, the time-dependent hazard ratio will be plotted in the form of a step function. All time-dependent analyses will be of an exploratory nature only.

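### Undated index-stay diagnoses count as baseline comorbidities, so conditions arising after surgery can pass as risk factors and, if onset differs by implant, be adjusted away

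*Combined protocol and SAP*

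**What the plan says.** Section 3.1 defines the baseline window: comorbidities are recorded "by including all outpatient and inpatient information coded within two years prior to the index hospitalization and during first hospitalization", apart from rows marked as exceptions. Four rows of Table 2 are limited to codes before admission: arthrosis, infection, elbow arthrosis and previous stroke ("I60-I69 (only before index admission"). Polytrauma is deliberately taken from the index stay only.

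Section 3.3 describes how these codes are dated: "ICD codes are all coded at the date of discharge and no chronological order within one case will be available".

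Section 4.2 puts the comorbidities to two uses. Matching is on, among other factors, "all clinical relevant comorbidities and pharmaceutical therapy at index hospitalization". In the outcome analyses, "a multivariable logistic regression model will be performed to adjust for" the patient's risk profile for binary endpoints, and for overall survival, MAE and TE "Multivariable Cox regression models will analyze the impact of baseline variables on the endpoints". Observation starts on the day of surgery.

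The stated aim has two parts: to compare TBW with LPF, and to identify independent risk factors for an unfavorable course.

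**The concern.** A baseline covariate should be fixed before treatment. Here part of the covariate record may come from after the operation, and nothing in the data can separate the two. Section 3.3 considers missing chronology only for complications, where it assumes that index-stay codes mostly reflect events after surgery. It does not consider the reverse error, in which a post-surgical diagnosis is counted as baseline.

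Two things are at stake:

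- **Risk factors.** If atrial fibrillation or heart failure is first coded because of an in-hospital infarction, cardiac arrest or sepsis, it will look like a baseline predictor of MAE. This needs no difference between the implants.
- **Treatment contrast.** If new onset of such a condition differs between TBW and LPF, balancing the arms on it removes that pathway from the comparison. Good z-difference balance would not reveal this, because the balancing is itself the error. The weighting analyses in section 4.3 change the weights and state no other covariate window.

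**Working it through.** The plan gives no figure on this point, so there is nothing to reproduce. The passages are compared first; two illustrations follow. All numerical inputs are assumptions.

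**Which open rows overlap a listed outcome?** The four restricted rows all share codes with an outcome in Table 2: arthrosis (M19 codes) and elbow arthrosis (M25.52) with minor outpatient complications, infection (T84, M86) with surgical infection, and previous stroke (I60–I69) with stroke (I60–I64). Two overlaps were left open:

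- Dementia, "F00, F01, F02, F05.1, G30, G31.1", contains F05.1, while the complication delirium is F05.
- Osteoporosis, M80–M85, contains the codes "M84.02, M84.22, M84.32, M84.82, M84.92" listed under minor outpatient complications.

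I48, I50, N19, F43 and Z74 are in no outcome definition. The concern with them is only that they may be first coded after surgery.

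**Illustration 1: risk factors.** Let the true prior prevalence be b = 10%, with no real effect on MAE. Among patients without the condition, a new code appears during the stay with probability q. The coded prevalence is c = b + (1 − b)q.

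- No MAE, q = 1%: c = 0.10 + 0.90 × 0.01 = 0.109; odds 0.109/0.891 = 0.122.
- MAE, q = 5%: c = 0.145; odds 0.145/0.855 = 0.170; odds ratio 0.170/0.122 = 1.4.
- MAE, q = 20%: c = 0.280; odds 0.280/0.720 = 0.389; odds ratio 0.389/0.122 = 3.2.

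The correct odds ratio is 1.0 in both cases.

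**Illustration 2: treatment contrast.** Suppose there is no other treatment effect, and the condition multiplies outcome risk by k. Then

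total risk ratio = [1 + c₁(k − 1)] / [1 + c₀(k − 1)],

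and it becomes 1.00 once the arms are balanced on the coded condition. With b = 10%:

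| New onset, arm 0 vs arm 1 | k | Calculation | Risk ratio removed |
|---|---|---|---|
| 1% vs 2% | 2 | 1.118/1.109 | 1.01 |
| 1% vs 2% | 4 | 1.354/1.327 | 1.02 |
| 2% vs 4% | 4 | 1.408/1.354 | 1.04 |
| 3% vs 5% | 3 | 1.290/1.254 | 1.03 |
| 2% vs 6% | 4 | 1.462/1.354 | 1.08 |
| 5% vs 10% | 4 | 1.570/1.435 | 1.09 |
| 2% vs 6% | 5 | 1.616/1.472 | 1.10 |

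Two variations show what drives the size:

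- **No prior prevalence (b = 0).** 3% vs 5% with k = 3 gives 1.10/1.06 = 1.04. 2% vs 6% with k = 5 gives 1.24/1.08 = 1.15. Setting b to zero inflates the result.
- **Weak effect on the endpoint (k = 1.2, b = 0).** The same onset pairs give 1.010/1.006 = 1.004 and 1.012/1.004 = 1.008. This is the more plausible case for local endpoints such as revision.

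If onset is equal in the two arms, the ratio is 1.00 and nothing is removed.

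**The case against.** The strongest reply is that the design is more careful than it first looks. The authors restricted the rows whose codes double as outcomes and kept acute renal failure (N17) and infarction (I21, I22) out of the baseline rows. Most open rows are chronic diseases, usually present before the fracture. The primary endpoints in Table 3 are largely local and often rest on dated OPS codes, and none of the disputed codes is a component of them. Delirium belongs to no composite or listed endpoint, and minor outpatient complications are counted only from outpatient codes after discharge. The two overlaps therefore blur what the covariate means more than what the endpoint counts. The documents also give no reason to expect wire or plate to change the onset of atrial fibrillation, heart failure or care dependency.

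Moving every such row to look-back only has a price as well. An uncoded condition is set to zero (section 5), so chronic disease first recorded at the index stay would become absent and confounding control would weaken. Prior level of care is available only from 2017, while inclusion starts in 2011, so for the earlier years Z74 is the only care-dependency row.

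All of this stands, and it limits reach and remedy. It does not answer the risk-factor problem, which needs no difference between arms, and no planned analysis would show whether the choice of window matters.

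**Conclusion.** The concern holds in a limited form. The window in section 3.1, the undated codes in section 3.3 and the use of these covariates in section 4.2 together allow post-surgical diagnoses into the propensity score and the models. Exposure is greatest for risk-factor estimates on MAE, TE and mortality. This includes 30-day mortality, which Table 4 lists as secondary and section 4.2 calls primary. The spurious odds ratios of 1.4 to 3.2 and the 1% to 10% shifts in the treatment risk ratio rest wholly on assumed frequencies. True size and direction cannot be known from the documents, and the effect is probably small for the primary local endpoints.

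Four stronger readings are tempting but not supported:

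- That matching removes part of any real TBW–LPF difference. It does so mainly if post-surgical onset differs by implant and the condition affects the endpoint.
- That the bias reaches 15%. That figure needs zero prior prevalence, a threefold difference in onset and a five-fold risk.
- That endpoints are matched on themselves. No disputed code is a component of a primary endpoint. M84 does overlap minor outpatient complications, but those are counted only after discharge.
- That patients aged 70 and over are most affected. The documents give nothing to show this.

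**What to change.** 1. In Table 2, apply the pre-admission limit already used for four rows to the overlapping codes left open: F05.1 in the dementia row and M84 in the osteoporosis row. The other codes in those rows can stay as they are.

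2. In section 4.3, prespecify one sensitivity analysis that rebuilds the propensity score, the matching and the outcome models from comorbidities coded in the two-year look-back only. Report it beside the main analysis for both treatment effects and risk factors. State in advance that a risk factor which disappears in this rerun will not be interpreted as a baseline predictor.

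I would not require I48, I50, N19, F43 and Z74 to be restricted in the main analysis. That is a trade-off against under-recorded chronic disease, and reporting both versions shows whether it matters.

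The cost is a change of date filter and one rerun. In the rerun some chronic disease first coded at the index stay is missed, although two years of inpatient and outpatient codes limit the loss. A risk factor can therefore also weaken there because true cases are missed, and the report should say so.

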The incidence of the olecranon fracture (OF) in adults is around 12 per 100,000 inhabitants per year.¹ The anatomical shape of the proximal ulna is largely responsible for the stabilization of the humeroulnar joint and reconstruction is therefore obligatory, but often challenging. Surgical treatment of the olecranon fracture is performed using tension band wiring (TBW) or locking plate fixation (LPF) osteosynthesis. It is not yet clear, which procedure is superior for a specific patient. In future, an individualized and objectified assessment of expected general and fracture-specific complications should enable the treatment to be individually adapted to the patient's risk profile. This shall prevent complications, unnecessary treatments, and treatment costs. In the project presented here, the reality of care for surgically treated patients with olecranon fractures will be analyzed using routine data collected by the BARMER health insurance fund.

The aim of the study is to analyze differences in the outcome of patients with an olecranon fracture treated with TBW compared to LPF and to identify independent risk factors for unfavorable course.

2. Population

The German reimbursement system governs the remuneration of health care services subject to encoded diagnoses (International Statistical Classification of Diseases, German Modification; ICD-10 GM) and procedures (German procedure classification – *Operationen- und Prozedurenschlüssel*; OPS) by means of the 'German Diagnosis Related Groups' taxonomy (GDRG). This obligatory documentation and accounting system is specified and further regulated in detail by mandatory coding instructions.

The database consists of retrospective health claims data of the German BARMER health insurance company. This includes anonymized data from following sectors:

- Inpatient data (§301 SGB V): In addition to information on costs, duration of hospitalization and information about treating hospital, standardized information on diagnoses (coded according to ICD-10 GM) and procedures (coded according to OPS) are available.
- Outpatient data (§295 SGB V): In addition to information on costs, diagnoses (ICD-10 GM) and procedures (OPS).
- Pharmaceutical therapies (§300 SGB V): Information on medication (coded via ATC classification), as well as costs and DDD (Defined Daily Dose).

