3.2. Endpoints

The following two sub-chapters list the primary and secondary endpoints to be analyzed together with their definition. For more information, as well as underlying ICP, OPS and ATC codes, see Chapter 3.1.

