3.2.1. Primary Endpoints

Variable	Definition
Revision	
 - Time from surgery to revision defined above.
Implant removal (only)	
 - Time from surgery to implant removal - Within first 3 months after surgery, an implant removal will also be considered as a surgical complication - No SC is allowed to occur within 3 months and on the same day
Surgical complications (SC)	
 - Time from surgery of OF to surgical complications, with death being considered as a competing risk event.
In-hospital SC rate (IH-SC)	
 - SC after surgery during index hospitalization (yes/no)
In-hospital implant-associated complications (IH-IAC)	
 - IAC after surgery during index hospitalization
In-hospital non-implant associated complications (IH-non-IAC)	
 - Non-IAC after surgery during index hospitalization

Table 3: Primary endpoints

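### On its natural reading, the plan counts only inpatient removals in the primary endpoint Implant removal (only), and no planned analysis shows what that leaves out

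*Combined protocol and SAP*

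**What the plan says.** Section 3.2.1 (Table 3) makes Implant removal (only) a primary endpoint, defined as "Time from surgery to implant removal", with the condition "No SC is allowed to occur within 3 months and on the same day". It does not say which care sector supplies the removals. Section 3.2 sends the reader back for detail: "For more information, as well as underlying ICP, OPS and ATC codes, see Chapter 3.1".

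Section 3.1 first reserves MOC for outpatient information coded after discharge, then sets the rule for the rest: "All other variables concerning complications during follow-up will be collected exclusively from inpatient information during hospitalization and after discharge". In Table 2 the two implant-removal rows (LPF and TBW) fall in the surgical-complications block and carry no note on sector. The Luxation row in the same block does carry one, adding the outpatient sector after discharge. The SC composite also contains early removal; its list opens "Adhesive capsulitis, arthrolysis, debridement, frozen elbow, implant removal within first 3 months, infection".

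Section 2 lists outpatient claims among the data held, including OPS procedure codes. The last row of Table 2 places the outpatient OPS codes listed earlier in the table into MOC, a secondary endpoint.

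Section 3.3, on bias from variable definitions, covers the timing of ICD codes and laterality. Section 4.3 repeats named regressions under different weights. Its endpoint list is OS, MAE, TE, SC, 30-day mortality, IH-MAE, IH-TE and IH-SC.

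**The concern.** A patient whose only removal was done as an outpatient would appear event-free on a primary endpoint, although the procedure code may be in the data. The TBW versus LPF p-value for that endpoint enters the Bonferroni-Holm family in section 4.2. Two consequences follow if outpatient removals exist. The reported removal incidence is too low in both arms. If surgeons or patients use the outpatient route to a different extent after TBW than after LPF, the comparison also shifts. Matching does not prevent this, because it balances baseline variables and not the setting of a later procedure. Sector is not mentioned in section 3.3, so a reader of the results would have no warning.

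**Working it through.** **Step 1: which sector applies.** Four parts of the plan bear on it.

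- Rule: section 3.1 confines follow-up complication variables other than MOC to inpatient information.
- Position: both implant-removal rows lie in the surgical-complications block of Table 2; the next block heading comes after them.
- Contrast: Luxation shows that an outpatient exception was written where one was wanted. The removal rows have none.
- Endpoint: Table 3 is silent on sector, and section 3.2 refers back to section 3.1.

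Together these point to inpatient only. One doubt remains. Table 3 classes a removal as a surgical complication only within the first 3 months, so a later removal is arguably not a complication and the section 3.1 rule may not reach it.

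**Step 2: where outpatient removals go.** The OPS row of MOC takes them in. MOC also contains a long list of ICD codes and the other outpatient procedures, and its clock starts at discharge, not at surgery. Section 4.2 compares MOC by arm only as a composite, so removals cannot be read from it.

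**Step 3: what would reveal the effect.** Section 4.3 varies the weights, not the data source, and does not list Implant removal (only). Reweighting cannot recover events that were not extracted.

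**Step 4: size.** The plan states no removal rate, sample size or outpatient share, so there is no figure to reproduce and every input here is assumed. Take the outpatient share *o* as constant over time:

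observed risk = true risk × (1 − *o*)

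observed risk ratio (TBW/LPF) = true risk ratio × (1 − *o*_TBW) / (1 − *o*_LPF)

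| Assumed true risk, TBW / LPF | Assumed outpatient share, TBW / LPF | Observed risk, TBW / LPF | Multiplier on risk ratio |
|---|---|---|---|
| 40% / 40% | 0% / 0% | 40% / 40% | 1.00 |
| 40% / 40% | 10% / 10% | 36% / 36% | 1.00 |
| 40% / 40% | 30% / 30% | 28% / 28% | 1.00 |
| 40% / 40% | 50% / 50% | 20% / 20% | 1.00 |
| 40% / 30% | 30% / 30% | 28% / 21% | 1.00 |
| 40% / 40% | 35% / 25% | 26% / 30% | 0.65/0.75 = 0.87 |
| 40% / 40% | 25% / 35% | 30% / 26% | 0.75/0.65 = 1.15 |

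With equal shares the risk ratio is preserved, but a true difference of 10 points shrinks to 7 (28% − 21%). With unequal shares a difference of 4 points appears where none exists, and its sign depends on which arm has the larger outpatient share. Risks are shown because section 4.2 names no model for this endpoint.

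**The case against.** The strongest reply is that section 3.1 makes a deliberate division: MOC from outpatient data, other complications from inpatient data. Outpatient procedures are then assigned, not lost, and section 4.2 compares MOC by arm with cumulative incidence functions, Gray's test and Fine-Gray models. The restriction may also have a reason, since section 3.3 accepts only ipsilateral OPS codes for SC and the documents do not say how completely side is coded in outpatient records. This part stands. It would be wrong to infer that outpatient removals vanish from the plan. What remains is that MOC does not isolate them.

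The second reply is that the documents never say that any removal is outpatient, or that the share differs by arm, and that the same rule governs Revision. This also stands, and it limits the claim. A reader might infer that the TBW versus LPF comparison is biased; the documents support only the conditional statement. Nor do they support a bias range, because such a range reflects the shares chosen. With true removal of 20%, 40% or 60% and HR = ln(1 − p_TBW)/ln(1 − p_LPF) under no true difference, shares of 0-20% differing by at most 5 points give 0.92-1.09. Letting shares run freely over 0-50% gives 0.39-2.57. Neither is an estimate for this study.

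A reader might also conclude that both sectors should form the main definition. That does not follow. Unknown outpatient laterality could exchange under-capture for events that cannot be attributed to the index elbow. An early removal is itself an SC, so a both-sector no-SC condition, read literally, could make it disqualify itself.

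**Conclusion.** The point holds in conditional form and should be fixed, with medium confidence. As the plan is most naturally read, outpatient removals are left out of a primary endpoint and of the 3-month removal component of SC, although outpatient procedure codes are held and are used for Luxation. The alternative reading, that later removals fall outside the section 3.1 rule, cannot be excluded. In that case the sector of a primary endpoint is unspecified, and two programmers could build it differently.

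Under-counting follows only if some removals are outpatient, and bias between arms only if the share differs by arm. Neither size nor direction can be derived from the documents. The 26% versus 30% example rests wholly on assumed inputs: 40% true removal in both arms, outpatient shares of 35% and 25%, and shares constant over time. This is more than a missing detail, because the stated rule would under-count a primary endpoint wherever removals are outpatient, and the plan has no analysis that separates those removals.

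**What to change.** 1. State the data sector for Implant removal (only) in Table 3, including for removals after 3 months.
2. Add to section 4.3 a sensitivity analysis that counts ipsilateral removal OPS codes from both sectors. Apply the no-SC condition in both sectors as well, and word it as SC other than the removal itself, so that an early removal does not disqualify itself.
3. Report the inpatient/outpatient split of removals by arm, and show removal codes as a separate line within MOC. Leave the MOC definition unchanged.
4. State in advance how outpatient removals without a coded side are handled, and show their number by arm.

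The cost is a few sentences in the SAP and a further extraction from data already held, covering the removal codes and the SC procedure codes that disqualify a removal. The drawback is that some outpatient removals may not be attributable to the index side; item 4 makes that visible.
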